will be randomized by order and the sequence of interventions will depend on whether a previous intervention has been administered. The participant may receive a minimum of zero adherence interventions over the 3 month period to a maximum of 5 adherence interventions during the 3 month period. A similar sequence of interventions will occur if patients experience a Glucose Failure. Finally, if subjects have both an Adherence Failure and a Glucose Failure at a checkpoint, they will enter the adherence intervention pathway. They will continue on this path until they have completed all three possible interventions. After this time, if they continue to failure both adherence and glucose targets, they will enter the glucose target intervention pathway. We decided that an adherence failure trumps a glucose failure because using the Auto Mode function is critical to opening the door to achieving glucose targets.

The figure below shows the possibilities at each 2-week checkpoint.

Figure 1. Potential interventions at 2 week monthly visit

[figure not shown]

Figure 1 above graphically depicts the treatment scheme for participants in the SMART. Below, the conditions and possible scenarios are described in more detail. As a reminder, there are five checkpoints (2, 4, 6, 8, and 10 weeks). At each checkpoint, here are the possible scenarios. A = adherence; G = glucose range; and R = randomization below:

1. If 1st A failure, R to A1, A2, or A3
2. If 2nd A failure (ie., there was a previous A failure), and a history of A3, R to A1 or A2
3. If 2nd A failure, with history of (respectively) A1(A2) give A2(A1).
4. If A success, 1st G failure, R to G1,G2,G3
5. If A success, 2nd G failure, w/ history of G3, R to G1,G2
6. If A success, 2nd G failure, w/history of (respectively) G1(G2) give G2(G1).
7. All else, no treatment.

As noted above, an Adherence Failure is defined as use of Auto Mode for less than 70% of the time at a checkpoint. A Glucose Failure is defined as spending less than 65% of the time in the 70 - 180 mg/dL range at a checkpoint. Also note that the final visit at 3 months is the end of the study and no interventions are offered at that study visit.

Study Group

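### The text moves families who keep failing both targets to the glucose pathway, but the numbered rules never treat them there; the 73% power also assumes exposure the rules cannot give

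*Combined protocol and SAP*

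**What the plan says.** Study Procedures describes the sequence twice.

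The running text covers a participant who fails both the adherence (A) and glucose (G) targets. That participant enters the adherence pathway: "They will continue on this path until they have completed all three possible interventions". Afterwards, "if they continue to failure both adherence and glucose targets, they will enter the glucose target intervention pathway". The text also sets a ceiling of 5 adherence interventions per participant.

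Seven numbered rules follow Figure 1, introduced by saying that "the conditions and possible scenarios are described in more detail". On the adherence side, a first failure is randomized among A1, A2 and A3. Then:
- Rule 2: "If 2nd A failure (ie., there was a previous A failure), and a history of A3, R to A1 or A2".
- Rule 3: "If 2nd A failure, with history of (respectively) A1(A2) give A2(A1)".

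On the glucose side:
- Rule 4: "If A success, 1st G failure, R to G1,G2,G3".
- Rule 5: "If A success, 2nd G failure, w/ history of G3, R to G1,G2".
- Rule 6: "If A success, 2nd G failure, w/history of (respectively) G1(G2) give G2(G1)".

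Rule 7 assigns no treatment in every remaining case.

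Biostatistics and Data Analysis describes the glucose randomization as two interventions and one control. It gives 73% power for a 10-point change for a given intervention, with 27 participants each assigned at least once to all three groups. It then concedes that tests of individual interventions are underpowered.

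**The concern.** The two descriptions give different treatment to the same family at the same checkpoint. Rules 4 to 6 all require adherence success and rule 7 excludes everyone else, so a family that still fails adherence cannot reach a glucose intervention. The text says it should. Five centers have to apply one algorithm, and the planned checkpoint-to-checkpoint models use the resulting assignments to judge which interventions work.

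The rules also conflict with the power statement. A participant first drawn to G1 or G2 can later receive only the other of those two, never G3. The 73% is therefore quoted for a pattern of exposure that the design does not produce. If G3 is the minimal intervention, the shortfall falls on the comparator for both active arms.

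**Working it through.** **Inputs from the plan.** Five checkpoints with possible intervention (weeks 2 to 10); rules 1 to 7; 27 participants with a glucose failure; difference 10 points; SD 15; alpha 0.05; power 0.9 with 26 for the whole group and 73% per intervention.

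**Assumptions.** Two-sided tests. First draws are equally likely, 1/3 each; the plan does not state the allocation, so the probability p of the third option is varied from 1/4 to 1/2. G3 and A3 are taken as the minimal intervention. This is inferred from the Minimal Intervention paragraph and the two-plus-one description of the glucose randomization; the written text does not label them.

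**Whole-group figure.** A one-sample t-test on change with n = 26, SD 15 and difference 10 gives power 0.904. The stated 0.9 is reproduced and is not questioned.

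**Failing both targets at all five checkpoints.** The rules do not say whether the second failure means exactly the second or any later one, so three readings are enumerated.

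| Version | Adherence interventions | Glucose interventions | P(all three A) | P(both A1 and A2) |
|---|---|---|---|---|
| Running text | 3 | up to 5 − 3 = 2 | 1 | 1 |
| Rules, exactly the second failure | 2 | 0 | 0 | 1/3 + 1/3 = 2/3 |
| Rules, any later failure, no repeats | 2 or 3 | 0 | 1/3 | 1 |
| Rules, A1 and A2 repeated | 5 | 0 | 1/3 | 1 |

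Glucose exposure is 0 on every reading of the rules. Under the two looser readings only those first drawn to A3 complete all three (25% to 50% over the range of p). The ceiling of 5 fits only the reading with repeats.

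**Glucose exposure, 27 participants who pass adherence and keep failing glucose.**
- G3 is given only at the first draw: 27 × 1/3 = 9, for any number of later failures and on every reading. Range: 27 × 1/4 = 6.75 to 27 × 1/2 = 13.5.
- G1 and G2 with two failures: 27 × (1/3 + 1/3 + 1/6) = 22.5 each, total 22.5 + 22.5 + 9 = 54.
- G1 and G2 with three failures, any-later reading without repeats: 27 each, total 27 + 27 + 9 = 63.
- The power statement implies at least 27 × 3 = 81.

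**Power, as illustration only.** The test behind 73% is not stated. Two groups of 27 with the stated SD of 15 give 67% by two-sample t, so 73% is not reproduced on that model. Solving for the SD that gives 73% yields 14.0. The table treats assignments as independent, with noncentrality 10 / (SD × √(1/n₁ + 1/n₂)).

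| Comparison | SD 14.0 | SD 15 |
|---|---|---|
| 27 v 27 (as the plan assumes) | 73% | 67% |
| Active v G3, 22.5 v 9 | 42% | 37% |
| Active v G3, 27 v 9 | 44% | 39% |

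With SD 14.0 and two failures, G1 or G2 receives 27 × (1 − p/2). Active v G3 is then 35% at p = 1/4 (23.6 v 6.75) and 50% at p = 1/2 (20.25 v 13.5). G1 v G2 is 65% (22.5 each) to 73% (27 each).

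**The case against.** The rules are presented as the fuller account, end in an exhaustive default, and fit the stated principle that an adherence failure takes precedence. They may well be what was built, and Figure 1, which was not available, may show it. A participant who regains adherence does reach rule 4, so the exclusion lasts only while adherence failure persists. The text's transfer needs three completed adherence interventions, so it can first apply at the fourth checkpoint, and the number affected is unknown. All of this limits the size of the problem. None of it makes the two instructions agree, and the plan does not say which governs.

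The reference to completing all three interventions is probably loose wording. If A3 is the control, not stepping down to it after an active intervention is sensible.

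On power, the objection is stronger. The plan explains its 10-point change as a move from baseline to completion, which could mean a pre-post test. With SD 15, a one-sample t-test gives 42% at n = 9, 85.5% at n = 22.5 and 91.5% at n = 27, so that reading does not yield 73% with 27 either. The planned growth-curve models use repeated measures within person, which a two-sample calculation ignores. The fall to about 40% is therefore not established, and for G1 and G2 even the direction of the error is open. The exposure count of 9 does not depend on any of this.

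The plan is a pilot, already calls these tests underpowered, and intends to size the next trial from observed effects. Restating 73% would not change that conclusion.

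**Conclusion.** The concern holds on both counts. First, the running text and the rules contradict each other for participants who keep failing both targets: up to 2 glucose interventions under the text, 0 under every reading of the rules. Second, the 73% rests on all 27 participants receiving each glucose condition, while the rules deliver G3 to about 9 (6.75 to 13.5). That count assumes equal first-draw allocation, with the range covering 1/4 to 1/2. Reading the shortfall as one in the control group assumes G3 is the minimal intervention. The recalculated power values illustrate a two-sample reading and are not corrected figures.

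This should be fixed, because treatment assignment has to be unambiguous in a trial whose objective is to compare interventions. It does not affect the whole-group baseline-to-completion analysis.

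**What to change.** Make one decision table operative for all sites and for the randomization system. Define A1 to A3 and G1 to G3, identify the minimal intervention, and say whether the second failure means exactly the second or any later one. Then choose one of these:

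- **(a)** Delete the two sentences on completing the adherence pathway and then moving to the glucose pathway, and keep rules 1 to 7.
- **(b)** Change the trigger to having received both active adherence interventions. Add a rule that participants who meet it and still fail both targets follow rules 4 to 6 without the adherence-success condition and with no step-down to control. This requires the any-later-failure reading; otherwise those first drawn to A3 never receive both active interventions.

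Reset the ceiling of 5 to match: under (a), 2 on the strict reading, 3 for any later failure without repeats, and 5 only if repeats are intended; under (b), 3.

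In Biostatistics and Data Analysis, drop the assumption that everyone receives all three conditions. Restate the per-intervention power from expected assignments per arm, naming the test and the SD.

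The cost is wording in two sections, a check of the randomization build and one recalculation. No participants or visits are added. Option (b) adds remote glucose sessions only for persistent dual failers, as the running text already intends.

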The primary effect we are interested in is percent change in the amount of time spent in the target glucose range from baseline to study completion. Data from our CGM study with toddlers (NIDDK funded DP3; [name] PI) show that of the sixteen 2-6 year-olds in the study they achieve, on average, only 45% time in 70-180 mg/dL target range (standard deviation = 15%). Our hypothesized change will be a 10% improvement in time spent in target range. There is sufficient power (0.9) to detect this change in a sample size of 26. Another aspect of calculating power in this study is the actual number of participants exposed to the planned interventions after a glucose “failure.” Over 90% of the participants in our DP3 toddler study experienced a glucose failure of less than 60% time in target range. Further, the table below shows the results of glucose failures from the DirectNet cohort of toddlers using CGM (Ped Diabetes 13:301-7, 2012).

Table 1. Expected Failure Rates

| | Months | | | | | | |
|---|--------|-----|-----|-----|-----|-----|-----|
| | 0 | 1 | 2 | 3 | 4 | 5 | 6 |
| Glucose Failure (not having at least 65% of readings in the 70-180 mg/dL range) | - | 70% | 70% | 70% | 70% | 75% | 75% |

The SMART design of our proposed study allows for randomization to one of 3 conditions when there is a glucose failure (2 interventions and 1 control). Because of this, participants can contribute to more than one comparison which increases power. This makes the SMART design very efficient, particularly when examining multiple treatment strategies, which is what clinicians do in these cases. Our primary outcome will be Glucose Failure, which we expect 80-90% of participants to experience. With 27 participants available for randomization after a Glucose Failure and each subject assigned at least once to each of the three intervention groups, there is only 73% power to detect a difference of 10% change in time spent in range for a given intervention. In other words, going from 45% time spent in range at baseline to 55% time spent in range at study completion; an outcome of 10% change. Thus, while the percent change in the sample from baseline to the end of the continuation phase does appear to be adequately powered for the group, the testing of individual interventions is underpowered. We will proceed with caution when estimating likely effect sizes for each intervention based on the results of the planned analyses.

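### Read literally, the glucose rules shut a child whose first Glucose Failure coincided with an Adherence Failure out of the G1/G2/G3 randomisation, against the plan's own prose

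*Combined protocol and SAP*

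**What the plan says.** The scenario list below Figure 1 in Study Procedures governs allocation at weeks 2, 4, 6, 8 and 10. On the glucose side it has four relevant lines:

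- Rule 4: "If A success, 1st G failure, R to G1,G2,G3".
- Rule 5: "If A success, 2nd G failure, w/ history of G3, R to G1,G2".
- Rule 6: "If A success, 2nd G failure, w/history of (respectively) G1(G2) give G2(G1".
- Rule 7: "All else, no treatment".

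The paragraph after the list gives the definition: "A Glucose Failure is defined as spending less than 65% of the time in the 70 - 180 mg/dL range at a checkpoint". It sets no condition on adherence. The prose before Figure 1 recognises that both failures can occur at one checkpoint and sends such a child to the adherence pathway, because "using the Auto Mode function is critical to opening the door to achieving glucose targets". The same prose makes the adherence sequence turn on what the family has already been given, and says glucose failures follow a similar sequence.

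Biostatistics and Data Analysis bases its power statement for single interventions on this entry point: "With 27 participants available for randomization after a Glucose Failure".

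**The concern.** Rules 4 to 6 are worded in terms of first and second failures. On the adherence side this is harmless, because rule 1 gives an assignment at every first A failure. On the glucose side an Adherence Failure can take precedence, so a first G failure may pass without a G assignment. The child then has a failure count of one and an empty G history, and no later rule fits that combination.

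The children affected are those whose Auto Mode use recovered while time in range did not. The plan treats adherence first because it is the route to glucose targets, yet the literal rules close the glucose interventions to families for whom that route worked. The G1/G2/G3 comparison would then cover mainly children whose first glucose failure came with adequate Auto Mode use, with fewer entrants than the plan counts on. If staff at different centres read rule 4 differently, similar children could also be allocated differently.

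**Working it through.** **The plan's figure.** The 27 equals 30 × 0.90. The plan shows no derivation. Both the upper end of its 80–90% expected glucose failure and its 10% dropout allowance give this number.

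**Tracing one child.** Week 2: both targets failed. This is a Glucose Failure by definition, and rule 1 gives an A intervention. Week 4: A success, G failure.

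- Rule 4 needs a first G failure; this is the second.
- Rule 5 needs a history of G3; there is none.
- Rule 6 needs a history of G1 or G2; there is none.
- Rule 7 applies: no treatment.

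A first G failure cannot recur, so the same holds for every later A-success/G-failure checkpoint. If '1st' and '2nd' refer to G assignments, or to G failures with A success, the child is randomised under rule 4 at week 4 and, if failing again, gets a second G intervention at week 6.

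**All histories.** Each checkpoint has four outcomes (A pass/fail × G pass/fail), so there are 4^5 = 1,024 histories. A history is affected when the first G failure falls at checkpoint k together with an A failure and a later checkpoint has A success with G failure. The count is the sum over k = 1 to 4 of 2^(k−1) × [4^(5−k) − 3^(5−k)]:

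175 + 74 + 28 + 8 = 285.

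Under either alternative reading the count is 0.

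**Size.** Inputs:

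- G failure g = 0.70, the months 1–3 value in Table 1, applied here to each two-week checkpoint (an assumption).
- A failure a: not in the documents; assumed 10%, 20%, 30% or 50% per checkpoint.
- Independence between A and G and between checkpoints (an assumption).

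Formulas:

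- Share affected = Σ(k=1..4) (1−g)^(k−1) · g·a · [1 − (1 − g(1−a))^(5−k)].
- Share reaching rule 4 under the literal rules = (1−a)(1 − 0.3^5) = 0.9976(1−a).
- Share reaching it if keyed to assignments = 1 − (1 − 0.7(1−a))^5.

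For a = 0.30: 0.1958 + 0.0546 + 0.0140 + 0.0028 = 0.267, and 30 × 0.267 = 8.0.

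| A failure (assumed) | Share affected | Affected of 30 | Affected of 40 | Reach rule 4, literal, of 30 | Reach rule 4, assignment-keyed, of 30 |
|---|---|---|---|---|---|
| 10% | 9.5% | 2.9 | 3.8 | 26.9 | 29.8 |
| 20% | 18.5% | 5.6 | 7.4 | 23.9 | 29.5 |
| 30% | 26.7% | 8.0 | 10.7 | 20.9 | 29.0 |
| 50% | 38.5% | 11.6 | 15.4 | 15.0 | 26.5 |

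The columns agree up to rounding. Both 30 and 40 are shown because the documents give both enrolment figures. Against 27/3 = 9 per arm at first glucose randomisation, the literal rules leave 20.9/3 = 7 at 30% and 15.0/3 = 5 at 50%.

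**Persistence.** If an A failure has an 80% chance of repeating at the next checkpoint, with the overall rate held at a (so a failure after a success has probability 0.2a/(1−a)), the number affected falls to about 1.5, 4 and 7 of 30 at 10%, 30% and 50%. Fewer children then recover Auto Mode in time to qualify.

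**The case against.** The strongest reply is that the gap is a matter of reading. Rule 4 can be taken as the first G failure that occurs with A success, and this closes the gap completely. Rules 5 and 6 between them cover G1, G2 and G3 histories, which suggests the authors took every second G failure to have a G history. Letting adherence take precedence also fits not counting the overridden glucose failure. All of this stands as evidence of likely intent. None of it is stated, and Figure 1, which might settle it, is not available here.

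A reader might infer that rule 2, "If 2nd A failure (ie., there was a previous A failure), and a history of A3, R to A1 or A2", proves that the ordinals count failures. It does not. Every first A failure brings an assignment, so on the adherence side counting failures and counting assignments give the same answer.

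A reader might also infer that an affected child gets nothing more at all. The rules do not support that: a further Adherence Failure can still bring an A intervention. Only access to G is lost.

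Nor do the documents establish a large loss. They give no adherence-failure rate. At 10% about 27 of 30 still reach rule 4, which equals the plan's own number, and persistence reduces the loss further. The study is a pilot that already calls its tests of individual interventions underpowered. The randomised contrasts among children who do enter G remain internally valid; what changes is whom they represent.

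Finally, the issue is not cleanly separate from the prose that keeps double failers on the adherence path until all three interventions are done. That text does not say whether adherence success releases a child.

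**Conclusion.** The point holds as a conflict between the literal rules and the prose, with a real consequence if the rules are programmed as worded. A child whose first Glucose Failure coincides with an Adherence Failure before any G assignment cannot enter glucose randomisation afterwards. The logic needs no assumed rate: 285 of 1,024 possible histories are affected, against none under either alternative reading. That count describes the rules and is not a probability.

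The expected number of children is uncertain. About 3 to 12 of 30 follows from assumed adherence-failure rates of 10% to 50%, a monthly 70% glucose-failure figure applied to two-week checkpoints, and independence; with the 80% persistence assumption it is about 1.5 to 7. The documents do not support saying that the trial intends this exclusion or that a particular share of the 27 is lost. They do support saying that the text permits it, that the loss would be selective, and that the wording should be settled before allocation depends on it.

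**What to change.** Reconcile rules 4 to 6 with the prose so that first and second on the glucose side refer to prior G assignments (equivalently, to G failures at checkpoints with A success) and not to all G failures. Keep the ordinals in rules 5 and 6: without them, a child who has had two G interventions would match those rules again, and what follows a second assignment would be undefined. Program the randomisation tool on the same definition and check that Figure 1 agrees.

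Settle this together with the prose on completing all three adherence interventions, including whether adherence success ends that path. If the sponsor did intend the exclusion, say so in the rules and revisit the 27.

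The cost is protocol wording in a few rules and a change to the randomisation logic. No extra visits, data or families are needed; some more remote sessions from the existing menu may be delivered.

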This adaptive study design employs the possibility of subsequent randomizations if pre-designated targets are not reached. All participants will be ages 2-6 years old and in the continuation phase of the Medtronic CEP 302 Trial using the Medtronic MiniMed 670G pump with Guardian 3 sensor. All subjects will receive the same standardized education on using the pump with hybrid closed loop capabilities and continuous glucose monitoring (CGM) during the initial Medtronic CEP 302 trial phase. A review session will also take place as they enter the extension phase of the study which is the beginning of this study. Their uploaded data will be reviewed every two weeks and if they are not meeting adherence ($\geq 70\%$ of the time in closed-loop) and glycemic target goals ($\geq 65\%$ of sensor values between 70 - 180 mg/dL), they will be randomized to six interventions: 1) reduce psychological distress, 2) reduce worries about hypoglycemia, 3) education and understanding of developmental and technologic demands for using hybrid closed loop this age group, 4) understanding and modification of carbohydrate to insulin ratios, set point and in depth nutritional education, and interventions 5) and 6) will be minimal interventions with a text message providing information on how they are doing at meeting their targets. All these interventions will be compared to a minimal intervention (text of their results compared to target goals). We will examine group differences over a 3-month period on health and psychological outcomes at baseline and after three months.

Objectives: The objective of this study is to assess several remote interventions with families in the extension phase of the 670G toddler study to determine which interventions are most effective in improving their time in target (70-180 mg/dl) and their adherence in maintaining closed-loop control (at least 70% of the time in closed-loop).

Sample Size:

- We anticipate enrolling at least 4 subjects at each of the current sites, and would like to expand the number of sites to include Yale, and the University of South Florida. Each of these sites is scheduled to enroll at least 4 toddlers, and some will enroll up to 8. We therefore anticipate being able to enroll at least 30 subjects. A sample size of 26 subjects should allow for a statistically significant result with a power of 0.9 and a p of 0.05. Enrollment of 30 subjects would allow for a 10% drop out rate. See Biostatistics and Data Analysis section.

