The study design is adaptive, specifically a SMART (sequential multiple assignment randomization trial). A SMART is an adaptive study design that allows for multiple assessments and based on the results of those assessments, a menu of interventions can be deployed. To ensure that there is no bias when interventions are delivered, and to have a test of whether those who receive the intervention fare better (or worse) from those who do not receive the intervention, a randomization strategy is used. The decision to use a SMART was primarily made because this is what happens clinically – a child (and family) start on a system with a certain dose of education and when problems arise, the clinical team offers interventions to optimize their use of the system. The SMART allows us to test which interventions are best for this patient population that presents many unique challenges for diabetes management and coordinated care from the team.

All participants will complete a *checkpoint* visit every 2 weeks for the duration of 3 months. At each checkpoint in the study (weeks 2, 4, 6, 8, and 10), data from the preceding 2 weeks will be reviewed to determine if there have been “failures.” Data will be available through pump uploads and by asking caregiver participants the frequency of wearing the devices. Objective data will guide determination of failures. We are defining failure in the following ways:

- 1) Adherence Failure: defined as using the hybrid closed loop “Auto Mode” less than 70% during a week
- 2) Glucose Failure: defined as less than 65% time spent in glucose range of 70 - 180 mg/dL.

If subjects pass both the adherence and glucose targets, no intervention is required. If there is an Adherence Failure, they will be eligible for an adherence intervention. The adherence interventions

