These sessions will primarily focus on parental concerns about hypoglycemia. In this age group we believe the major focus will be on fear of hypoglycemia, but we will also provide education and support on safely reducing hyperglycemia. Since many of these families may have previously used the Dexcom share with remote monitoring, we will discuss how they may or may not be using the Dexcom Share for remote monitoring since this feature is not available on the 670G pump. We will review their fears and the child's past severe hypoglycemic events, and what they have read and heard from friends and support groups. We will teach parents the links between fears/worries and diabetes behaviors (e.g., fear may lead to hyper vigilance which in turn causes more stress and burnout). We will provide behavioral strategies for monitoring for hypoglycemia (and hyperglycemia) at regular intervals, steps to problem solve unexpected high and low blood sugars, and basic efforts at sleep hygiene. These sessions have the same format (two \approx 30-minute sessions delivered online or over the phone).

Minimal Intervention

The randomization to minimal intervention will be present in both the Adherence arm and Glucose arm. In this intervention the parent will receive either an email or text message that details what percentage of the prior two weeks spent in Auto Mode, percentage of time below, within, or above target glucose range, and whether they met the study goals for these areas. If they have concerns about their management, they are of course instructed to contact their study coordinator or study PI.

Study Visits and Measurements

In person study visits for all participants will occur at baseline (0 weeks) and 12 weeks. These are the pre and post assessments that include all measures in table 2 below. Briefer assessments (or checkpoints) are completed at 2 weeks intervals. These visits should be within ± 1 week of the scheduled visit. Any behavioral interventions delivered will be done remotely and will not require an in-person visit. All of the questionnaires will be completed online via RedCap.

Table 2. Timeline and Components of Study Visits and Checkpoints

| Visit/Checkpoint | 1 | 2 | 3 | 4 | 5 | 6 | 7 |
|---|-----------|-------|-------|-------|-------|-------|-----------|
| Study Time: | 0 | 2w | 4w | 6w | 8w | 10w | 12w |
| In-person or remote | In-person | Phone | Phone | Phone | Phone | Phone | In-person |
| History (medical and demographic) | X | | | | | | |

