| Satisfaction with Glucose Monitoring | The Glucose Monitoring System Satisfaction Survey (GMSS-T1D) is a validated tool used to assess treatment satisfaction with glucose monitoring devices and its impact on quality of life and other patient-reported outcomes. | 15 items. 5-10 minutes to complete. |

| | | |
|---------------------------------|--|--|
| Use and Comfort with Technology | Objective questions documenting the frequency of use and types of technologies used. Both general (e.g., smartphone) and diabetes-specific (e.g., trend program). | 23 items. 5 minutes to complete. |
| Demographic and Family Data | Parents will complete a questionnaire on the family's structure, racial and ethnic background, indicators of socioeconomic status, insurance status (public vs. private), and other essential characteristics. | 5 minutes |
| Behavioral Outcomes | | |
| Diabetes management behaviors | Amount of time spent in Auto Mode; blood glucose monitoring frequency (by meter download); adherence to pump boluses; | Download (no time burden for participants) |
| Health care utilization | Number of visits and calls to the diabetes care team | Tracking by interview (10 minutes to complete) |

Table 4. Measures obtained from child

| | | |
|-----------------------------|--|---|
| Health Outcomes | | |
| HbA1c measurement | Participants will provide a small fingerstick sample of blood (capillary) during their routine clinic visit. This will be done using the DCA in clinic or local lab method. | Gold standard measure of glycemic control |
| Glycemic excursion measures | Time in range (70 to 180 mg/dL); percent below 70 and 60 mg/dL as indicators of hypoglycemia, and above 180 and 250 mg/dL as indicators of hyperglycemia; additional indices of variability including standard deviation will also be calculated | |

In addition, parents will be asked to complete a brief online survey (< 10 minutes) at the following intervals since randomization – 4, 8, and 12 weeks. These online surveys will consist of the Diabetes Distress Scale (3 items), PHQ-8 (8 items), and the short form of the STAI (10 items). All surveys can be completed online via RedCap.

Schedule

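### The brief parent surveys are timed from randomisation, but families are randomised only on failure at weeks 2 to 10 or never, so the schedule does not fit the 12-week study

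*Combined protocol and SAP*

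**What the plan says.** Under Study Visits and Measurements, after Table 4, parents are asked for a short online survey "at the following intervals since randomization – 4, 8, and 12 weeks". It consists of three diabetes-distress items, the PHQ-8 and a ten-item STAI.

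Randomisation is described in the Synopsis and under Study Procedures, and it always depends on failure:

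- The Synopsis says that if families miss the adherence and glucose goals "they will be randomized to six interventions".
- Study Procedures sets the times: "At each checkpoint in the study (weeks 2, 4, 6, 8, and 10), data from the preceding 2 weeks will be reviewed". It repeats them before the scenario list: "As a reminder, there are five checkpoints (2, 4, 6, 8, and 10 weeks".
- The scenario list gives the triggers: "If 1st A failure, R to A1, A2, or A3" on the adherence path and "If A success, 1st G failure, R to G1,G2,G3" on the glucose path. A second failure after A3 or G3 leads to a further randomisation.
- Families who meet both targets receive no intervention.

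Study Procedures also says that "the final visit at 3 months is the end of the study" and that no intervention is offered there. Study Visits and Measurements places that visit at week 12, with a visit window of one week either side.

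The visit schedule ("Table 2. Timeline and Components of Study Visits and Checkpoints") has a row for the full psychosocial questionnaires at weeks 0 and 12. It has no row for the brief survey.

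**The concern.** A schedule counted from randomisation works when everyone is randomised on entry. Here the starting point is itself an outcome: it exists only if a family fails, and its date depends on when. A family may also be randomised more than once, and the text does not say which randomisation starts the clock.

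At stake are the only psychosocial data planned between weeks 0 and 12. Distress Reduction is one of the interventions under test, so the brief survey is the plan's only interim view of what that intervention is meant to change. Followed as written, whether and when a family is surveyed depends on its glucose and adherence results. Families who succeed throughout supply nothing, and late failers supply little or nothing within the study. With five sites, coordinators could also interpret the trigger differently.

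**Working it through.** **Inputs.** Survey intervals k = 4, 8, 12 weeks (text after Table 4). Possible first-randomisation weeks r = 2, 4, 6, 8, 10 (Study Procedures). End of study at week 12, visit window one week either side (Study Visits and Measurements). Expected share with a glucose failure 80-90% (Biostatistics and Data Analysis).

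**Step 1: nominal dates.** Survey week = r + k, taking randomisation on the day of the checkpoint.

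| First randomised at week | 4-week survey | 8-week survey | 12-week survey | Dates by week 12 |
|---|---|---|---|---|
| 2 | 6 | 10 | 14 | 2 |
| 4 | 8 | 12 | 16 | 2 |
| 6 | 10 | 14 | 18 | 1 |
| 8 | 12 | 16 | 20 | 1 |
| 10 | 14 | 18 | 22 | 0 |

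The 12-week survey falls at weeks 14 to 22, never by week 12. The 8-week survey fits for r = 2 or 4 only, and the 4-week survey for r = 8 or earlier. In all, 2 + 2 + 1 + 1 + 0 = 6 of the 15 possible dates fall by week 12.

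**Step 2: which randomisation.** First randomisation is the most favourable reading. Starting the clock at a later one moves every date later.

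**Step 3: visit window.** A week-2 checkpoint held at week 1 puts the 12-week survey at 1 + 12 = 13, the same week as a final visit held at its latest, 12 + 1 = 13. The other two nominal week-14 dates have the same edge case: 5 + 8 = 13 and 9 + 4 = 13. No date at week 16 or later can be rescued this way.

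**Step 4: families with no date.** If 80-90% have a glucose failure, 10-20% do not. That is 30 × 0.10 = 3 to 30 × 0.20 = 6 families of 30, or 4 to 8 of the 40 given under Study Procedures and Study population. It is an upper bound on the never-randomised, since some of these families may be randomised for an adherence failure. It takes the expected failures to occur at weeks 2 to 10.

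**Step 5: the same intervals from baseline.** 0 + 4, 0 + 8 and 0 + 12 give weeks 4, 8 and 12. These are visits 3, 5 and 7 in Table 2, and they exist for every family.

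**The case against.** The strongest reply is that the word is a slip. Weeks 4, 8 and 12 coincide with Table 2 visits when counted from entry. Study population speaks of randomising all 40 families, and the Synopsis refers to later randomisations as though there had been an earlier one. This is plausible, but neither passage sets a randomisation date at entry, and the scenario list excludes families who pass. If it is a slip, the correction is the same.

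A reader might infer that the comparison of psychological outcomes between baseline and three months rests on a sample selected by outcome. The documents do not support that. Table 2 gives the full battery to all participants at weeks 0 and 12, and Table 3 shows that it includes the PHQ-8, the 40-item STAI and two diabetes-distress scales. The brief surveys are supplementary, and no stated analysis uses them: the models under Biostatistics and Data Analysis concern time in range.

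Nor is 6 of 15 an estimate of data loss. It counts possible dates with equal weight. Table 1 expects 70% glucose failure already at month 1, so first randomisations should cluster early, where two of the three surveys fit.

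These replies limit the harm, but they do not make the schedule workable as written.

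**Conclusion.** The point holds as a fault in the survey schedule. On the nominal timetable the 12-week survey falls two to ten weeks after the study ends (14 - 12 = 2, 22 - 12 = 10). Families first randomised at week 10 have no survey within the study, and at most 10-20% of families have no date at all. It would be too strong to say that the 12-week survey can never coincide with study participation: at the edge of the visit window it can fall on a final visit held at week 13.

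The damage is confined to the interim psychosocial data, which would come only from families that failed, at differing study weeks. The primary outcome, the sample size and the comparison of week 0 with week 12 are untouched. The conclusion assumes that the failure-triggered randomisations are the only ones and that each takes place at its checkpoint. The 10-20% bound also rests on the plan's own failure expectation.

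**What to change.** In the sentence after Table 4, count the intervals from the baseline visit (week 0) instead of from randomisation, so that every family is surveyed at study weeks 4, 8 and 12. Add a brief-survey row to Table 2 at visits 3, 5 and 7. For week 12, state whether the PHQ-8 and STAI in the full battery serve in place of the overlapping brief items. Record the date of each randomisation so that time since randomisation can be derived.

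The cost is one sentence, one table row and the REDCap trigger date. The downside is that surveys no longer fall at a fixed interval after an intervention. A family first randomised at week 10 would have only the week-12 survey afterwards, about two weeks later. Recorded dates describe that short follow-up but cannot recover a response at 4 or 8 weeks.
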